#### 2.3.2 Known Potential Benefits

Potential benefits to participants in this study will include the opportunity to learn about the potential benefits of new technology and gaming for improving upper extremity function in children with hemiplegia. The knowledge gained from this study may lead to substantial benefits for both individuals (in improving motor function and functional independence) and society (by increasing access to and reducing the cost of care). Subjects assigned to the MOVE-IT HEP group may benefit from participation by improved UE motor status. Subjects assigned to the UCT group will be offered access to the MOVE-IT HEP following completion of participation as a control.

# 3 OBJECTIVES

The primary Phase II investigational objective is to show a differential effect on the pre-to-post-intervention change in upper extremity (UE) motor function between an interventional group receiving the MOVE-IT home exercise program (HEP) and a usual care treatment (UCT) group, as assessed by the Jebsen Taylor Hand Function Test (JTHFT) and other gold-standard clinical assessments of UE function.

Blinded assessors, certified for the study instruments, will evaluate children in both groups at pre-treatment (baseline), immediate post-treatment (baseline + 10 weeks), and 3 months post-treatment. Assessments (3 total) will take place in an outpatient setting and include the following blinded instruments:

- Jebsen Taylor Hand Function Test (JTHFT) (primary outcome measure)
- Quality of Upper Extremity Skills Test (QUEST) (dissociated movements and grasp components)
- Wolf Motor Function Test (WMFT)

Additionally, parents will be asked to complete the following parental report instrument during each assessment visit:

• Pediatric Motor Activity Log (inventory of child's functional use of the UE)

For both groups, parents will be asked to maintain a weekly activity log, including activities performed under the MOVE-IT intervention and any other therapy a child might receive.

#### 4 STUDY DESIGN

The study is a randomized control study.

Following screening, enrolled subjects will be randomized to either the MOVE-IT home exercise program (HEP) or usual care treatment (UCT) group using a centralized and masked process developed by the study biostatistician. The HEP group is the interventional group. The UCT group is the control group. Following the control strategy previously adopted in the Children with Hemiparesis Arm and Movement Project (CHAMP) multi-site RCT (NICHD R01, trial registration number NCT01895660), children in the UCT group will be followed as they continue to receive their previously prescribed therapy services. As UCT group participants, these children will not receive any treatment services through the study. Parents will be asked to report therapy services their children receive during each assessment visit.

To ensure that an approximately equal number of subjects are randomized to the MOVE-IT HEP and UCT groups throughout the Phase II enrollment period, we will randomly assign the patients to the two study-groups in accordance with a permuted block randomization scheme. The randomization list will be generated by a UVA study biostatistician ([name]) using the PLAN procedure of SAS (SAS Institute Inc., Cary, NC). One subject randomization table will be generated for each site. The group assignment will be blinded to the therapists (raters) who perform the pre- and post-assessments. The group assignment will be not be blinded to the participants. The non-rater members of the IRB-approved study team will have access to the randomization list.

Demonstration of statistically significant improvement in UE motor function for participants the MOVE-IT HEP versus UCT will support the validity of MOVE-IT use as an intervention for children with hemiplegia. In home use, MOVE-IT will enable more frequent and intensive therapy with reduced travel and may extend the service range of existing rehabilitation providers to include underserved areas. In clinical practice, MOVE-IT will enable new models of delivery based on remote monitoring combined with outpatient services, increasing quality and efficiency of care. Statistical considerations for sample size determination, primary analysis, and secondary analyses are described below.

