#### ALL - Outpatient Visit 1: Pre-Assessment (will last about 90 minutes)

- Blinded study therapist will review consent and re-verify inclusion and exclusion criteria
- Blinded study therapist will administer clinical tests for UE function
  - Jebsen Taylor Hand Function Test (JTHFT) (primary outcome measure)
  - Quality of Upper Extremity Skills Test (QUEST) (dissociated movements and grasp components)
  - Wolf Motor Function Test (WMFT)

- If administration of the test instruments cannot be completed for any reason (e.g. subject becomes fatigued), the participants may be asked to return for an additional visit to complete the procedures. The participant will be provided the normal per-visit stipend for the additional visit.
- Subject will be assigned to either the MOVE-IT HEP or the UCT group employing the study randomization procedure and scheduled for remaining visits.

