## 7.3 Participant Enrollment and Follow-Up

Approximately 24 subjects will be recruited at each of the two sites (48 total). Recruited children will have a diagnosis of hemiplegia resulting from cerebral palsy, stroke, or other form of brain injury; be between 4 and 14 years of age; have no history of uncontrolled seizures; and be medically stable. Children will be excluded if they received botulinum toxin injections, stem cell infusions or another form of intensive UE therapy, such as CIMT, within the prior 6 months. Children may receive other forms of treatment or intervention during and after the MOVE-IT intervention; data about such other interventions will be collected prospectively from parents.

It is expected that participant enrollment in the MOVE-IT Phase II RCT will be open for a period of approximately 10 months. Monthly enrollment is projected to average from 6-12 new subjects per month across both sites. Each subject's participation includes a 10-week interventional (or control) period and a 3-month follow-up assessment.

An approximately equal number of subjects will be recruited at the UVA Children's Hospital (n=24) and the Duke Children's Hospital (n=24) study sites, facilitated by experienced study coordinators at each site. Based on recent completion of studies of similar scope, including the CHAMP CIMT trials at UVA [12], the team anticipates being able to meet the MOVE-IT RCT goals.

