All biostatistical design and analysis will be conducted by [name], a Pstat accredited Senior Biostatistician within the Department of Public Health Sciences of the University of Virginia School of Medicine.

Data from the UVA and Duke sites will be combined during analysis. Randomization will be done at each site. Variation between the two sites is expected to be minimal. The effect of the treatment to be tested is expected to be the same among the two sites, which

will use identical protocols.

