#### Consent Visit (in-person or remotely administered, will last about 45 minutes)

- The child and a parent/guardian will take part in remotely-administered telehealth visit with a study coordinator or a study therapist by phone or HIPAA compliant video conferencing (e.g. Zoom Health) OR take part in-person.
- Participants will be asked pre-screening questions to verify inclusion and exclusion criteria.
- Participants at the University of Virginia will complete informed consent and assent using DocuSign or alternative institutionally-approved method.

-	Participants at Duke University will complete informed consent and assent using a wet signature if the consenting meetings takes place in-person, such as in clinic. If the consenting process takes place via HIPAA compliant video conferencing or phone, study staff will direct the parent/guardian to sign the consent in the appropriate spaces. Study staff will then provide a mailing address for the participant to send the completed consent form. Duke study staff will document the reason remote consent was obtained (i.e. in-person consent not possible due to distance from Duke University).

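### Section 4 opens the pre-generated randomization list to non-rater staff without limiting access to assignments already made, so allocation concealment is not assured by the text

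*Combined protocol and SAP*

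**What the plan says.** Section 4 describes assignment "using a centralized and masked process developed by the study biostatistician". It then specifies permuted blocks and states: "The randomization list will be generated by a UVA study biostatistician", followed by "One subject randomization table will be generated for each site". The list is therefore a complete object produced in advance. After saying that raters are blinded to group and participants are not, the section adds: "The non-rater members of the IRB-approved study team will have access to the randomization list".

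Three other places bear on who those staff are and when assignment happens:

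- Section 7.3 says that recruitment at both sites is "facilitated by experienced study coordinators at each site".
- Under the Consent Visit in Section 9, the family may "take part in remotely-administered telehealth visit with a study coordinator or a study therapist".
- Section 6.1, Outpatient Visit 1, says: "Blinded study therapist will review consent and re-verify inclusion and exclusion criteria". Assignment to group is the last item listed for that visit, after the baseline tests.

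The available text does not state a block size or a mechanism for releasing assignments. The Key Roles section and the study-plan figure are not in the text available for review and may say more.

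**The concern.** Allocation concealment requires that whoever decides whether and when a family enters cannot know the next assignment. Rater blinding is a different protection: it guards the measurement of outcome but not the make-up of the arms. If staff who approach, consent or book families can see upcoming rows, the order of entry and the way the study is presented can depend on the arm that comes next. Children expected to do well could then be placed more often in one arm.

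Bias of this kind enters before baseline. Covariate adjustment removes only the part that the measured covariates capture. The trial is small (24 dyads per site), open to families and non-rater staff, and rests on a between-group comparison. Several exclusion criteria also depend on judgement. The later offer of MOVE-IT to control families (Sections 2.3.2 and 6.1) lessens the motive to steer but does not remove it.

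**Working it through.** **Step 1: the text.** Section 4 uses the term randomization list twice. The first use is the list generated by the biostatistician; the second is the object that non-rater staff may see. No wording separates the two, so the plain reading includes future rows. Coordinators are nowhere described as raters, they facilitate recruitment, and they may run the consent visit. They therefore appear to fall within the group given access. That overlap is inferred from how the roles are worded; the plan does not state it.

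**Step 2: the plan's own figures.** The plan gives no figure on concealment. The only inputs taken from it are 20 completers per group (Section 7.2) and the 0.05 level (Sections 7.2 and 7.4), treated as two-sided. The recruitment arithmetic reproduces: 20 / 0.85 = 23.5, so 24 per group and 48 in all. The sample size is not in dispute.

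**Step 3: an illustration of size.** All the inputs here are assumptions:

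- On a fraction f of slots, staff choose between two waiting families. The one with the better perceived prognosis enters MOVE-IT and the one with the worse enters usual care.
- Perceived prognosis correlates r with change in the outcome, and 0.5 with the baseline score.
- The true effect is zero.

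The expected maximum of two standard normal values is 0.5642, so the expected spurious difference is 2 × 0.5642 × r × f standard deviations (SD). For r = 0.5 and f = 0.5 this is 0.28 SD. Simulation with 200,000 trials per setting gives:

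| r | f | Shift (SD) | Rejection, unadjusted | Rejection, ANCOVA on baseline |
|---|---|---|---|---|
| any | 0 | 0 | 0.050 | 0.050 |
| 0.2 | 0.25 | 0.06 | 0.054 | 0.052 |
| 0.2 | 0.50 | 0.11 | 0.064 | 0.058 |
| 0.3 | 0.25 | 0.08 | 0.058 | 0.055 |
| 0.3 | 0.50 | 0.17 | 0.082 | 0.069 |
| 0.5 | 0.25 | 0.14 | 0.072 | 0.063 |
| 0.5 | 0.50 | 0.28 | 0.143 | 0.103 |

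These runs discard the family not chosen. If that family stays in the queue (two sites, block size 4 assumed), the same settings give 0.055 to 0.187 unadjusted and 0.053 to 0.133 by ANCOVA.

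**Step 4: does limiting access to past assignments suffice?** Suppose staff see only past assignments but know a fixed block size. With 24 per site, the share of assignments that is certain, and the accuracy g of the best guess, are:

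- block 2: 50% certain, g = 75%
- block 4: 33% certain, g = 71%
- block 6: 25% certain, g = 68%
- block 8: 20% certain, g = 67%

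With the full list, 100% are known. A wrong guess steers the wrong way, so the part of the shift that remains is 2g − 1. This is 0.50 for block 2 and about 0.42 for block 4. The 0.28 SD shift falls to about 0.14 SD and 0.12 SD. Restricting access alone leaves roughly 42% to 50% of the modelled shift at these two block sizes, which is why the fix must also deal with block size.

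**The case against.** The strongest reply is that the sentence follows directly on two statements about who is blinded to group. It may therefore only name who is unblinded, and the section already calls the process centralized and masked. This reading is possible and cannot be excluded. It does not remove the point: being told an assignment already made is different from having the list, and the text grants the list. The description of the process states an aim without a mechanism, and the access sentence undercuts it.

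Second, Section 6.1 refers to a study randomization procedure, so operational detail may exist elsewhere. It also has a blinded therapist re-check eligibility, with assignment listed after the baseline tests. These are real safeguards, but they come after prescreening, the consent discussion and booking.

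Third, the size in Step 3 rests wholly on assumption, and every steered slot is taken to favour MOVE-IT. Section 7.4 plans ANCOVA, though without naming covariates. If baseline is one of them, five of the six settings with steering give 5.2% to 6.9% in the main model. This stands, and the figures should be read only as a range of possibilities.

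A reader might infer that concealment is absent, or that staff do steer enrolment. The documents support neither. They contain two statements in tension and no evidence of misuse.

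**Conclusion.** The point holds as a gap in the written plan. Followed literally, the access rule in Section 4 exposes upcoming assignments to staff who may recruit and consent, and it conflicts with the masked process that the same section describes. Confidence is medium, because the sentence may have a narrower intent and the overlap of roles is inferred.

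Any inflation of the false-positive rate is hypothetical. It runs from negligible to material depending on how often staff could steer and how well they could judge prognosis. The 14% unadjusted figure (up to about 19% in the queue version) is the corner of an assumed range and not an estimate for this trial.

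The statement in Section 7.4, "Randomization will be done at each site", might be read as contradicting a centralized process. It is equally consistent with a separate table for each site and is not part of the defect.

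The change should be made, because it is cheap and later analysis cannot fully repair a failure of concealment.

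**What to change.** Replace the access sentence in Section 4 with wording to this effect:

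> The full allocation schedule is kept solely by the study biostatistician or a central system, neither of which takes part in recruitment. Each assignment is released one at a time, once consent, eligibility re-verification and baseline assessment have been recorded. Unblinded staff may see only assignments that have already been made. Block sizes vary and are not disclosed to site staff.

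If this is already the practice, only the text changes. Optionally, Section 7.4 could say that randomization at each site means a separate table per site, if that is the intent.

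The cost is a short wait for each assignment and a slightly more complex list. Sample size, endpoints and analysis are unaffected. The change makes assignments harder to predict, but in an open-label trial with blocks within site it does not guarantee that they cannot be predicted.

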#### 5 STUDY POPULATION

#### 5.1 Selection of the Study Population

Ages: 4 - 14 years (inclusive)

Sex: Any Race: Any

Target # of subjects (at all sites) needed to complete protocol: 40.

Expected rate of screen failure/ dropouts/withdrawals from all sites: 15%.

Number of subject/dyads to be enrolled at all sites: 48.

Number of subjects who will sign a consent form under this protocol: 48 dyads.

(24 at UVA and 24 at Duke)

#### 5.2 Inclusion/Exclusion Criteria

#### Criteria for inclusion

- (1) Diagnosis of hemiplegia resulting from cerebral palsy, stroke, or other form of brain injury;
- (2) Medically stable;
- (3) Manual Abilities Classification System (MACS) rating between II and V; indicating the child experiences mild to severe difficulty in handling objects with the affected hand;
- (4) Communication Functional Classification System (CFCS) rating between I and III; indicating the child usually communicates effectively with familiar communication partners, but not unfamiliar partners, in most environments;
- (5) Participant has antigravity strength in the affected UE at the elbow to at least 45 degrees of active flexion;
- (6) Participant has antigravity shoulder strength in the affected UE to at least 30 degrees each in active flexion, abduction/adduction, and 15 degrees in active internal/external rotation when in an upright and seated position;
- (7) Participant has ability to perform a basic color-matching test and identify characters on a vision chart;

- (8) Participant must be available to attend study visits;
- (9) Willingness and ability to comply with scheduled visits and study procedures.

#### Criteria for exclusion

- (1) History of uncontrolled seizures;
- (2) Has received botulinum toxin injections, stem cell infusions or another form of intensive UE therapy, such as CIMT, within the prior 6 months;
- (3) Unwillingness or inability to understand or follow verbal directions;
- (4) Diagnosis of moderate to severe cortical-visual impairment that in the judgement of the Principal Investigator could adversely impact the subject's participation;
- (5) Psychological diagnosis that in the determination of the Principal Investigator could significantly impact subject's participation or that could be aggravated by study participation;
- (6) Determination that participation would result in over exertion, or significant discomfort or pain;
- (7) Determination that participation would result in significant agitation or elevated stress;
- (8) Visual field deficit in either eye that impairs the ability to view the computer monitor.

Restrictions on use of other drugs or treatments: None

# 5.3 Subject Compensation

Participants will be compensated for being in this study.

Participants will be paid a \$50 stipend for each outpatient visit completed (3 total visits). Participants will not be compensated for home visits.

If a participant drops out or is otherwise disenrolled form the study, payments will be pro-rated based on number of visits completed (\$50 per outpatient visit).

Participants will not receive reimbursement for actual expenses related to being in this study (e.g. travel).

#### **6 STUDY PROCEDURES/EVALUATIONS**

# 6.1 Study Procedures

Identical procedures will be followed at the UVA and Duke sites.

Prior to consent, candidates will be contacted by phone and the parent/guardian asked to respond to questions pertaining to eligibility (inclusion/exclusion criteria). For example:

- Does the child have a history of uncontrolled seizures?
- Has the child received botulinum toxin injections, stem cell infusions or another form of intensive arm therapy, such as CIMT, within the prior 6 months?
- Can the child move the affected arm and flex the elbow about halfway?
- Is the child's corrected vision good enough to comfortably watch a TV show for 30 minutes?

The final list of questions will be included in a telephone recruitment scripts that will be submitted for IRB approval prior to use. After prescreening using the IRB-approved script, candidates will be scheduled for a remotely-administered consent and screening telehealth visit and for a pre-assessment visit.

- The parent/guardian will be asked to complete the following parental report instrument:
  - o Pediatric Motor Activity Log (inventory of child's functional use of the UE)

#### ALL - Outpatient Visit 1: Pre-Assessment (will last about 90 minutes)

- Blinded study therapist will review consent and re-verify inclusion and exclusion criteria
- Blinded study therapist will administer clinical tests for UE function
  - Jebsen Taylor Hand Function Test (JTHFT) (primary outcome measure)
  - Quality of Upper Extremity Skills Test (QUEST) (dissociated movements and grasp components)
  - Wolf Motor Function Test (WMFT)

- If administration of the test instruments cannot be completed for any reason (e.g. subject becomes fatigued), the participants may be asked to return for an additional visit to complete the procedures. The participant will be provided the normal per-visit stipend for the additional visit.
- Subject will be assigned to either the MOVE-IT HEP or the UCT group employing the study randomization procedure and scheduled for remaining visits.

#### **GROUP 1: MOVE-IT HEP GROUP**

#### MOVE-IT HEP Visit 1 (will last about 90 minutes)

- A non-blinded study team member will conduct a home visit at the patient's residence.
- The team member will either drop off the system with the family OR set up the MOVE-IT system in the home and verify safety of the system setup.
- A therapist will guide the patient in practice using the MOVE-IT system either in-person at the home or via approved telehealth connection. The therapist will provide training to the parent/guardian either in-person in the home or via approved telehealth connection.

#### MOVE-IT HEP Home Visit 2 (will last about 60 minutes)

- A non-blinded study therapist will conduct a second home visit at the patient's residence or meet with the subject via approved telehealth connection.
- The therapist will observe the patient in practice using the MOVE-IT system and provide additional guidance and training as needed.
- If on the study therapist's recommendation, the study PI determines an additional visit is warranted to ensure a patient can safely and successfully use the system at home, an additional visit will be conducted either in the home or via an approved telehealth connection.

#### MOVE-IT HEP Independent Practice at Home

- Participants will be asked to employ the GRASP system for UE practice at home for a total of 1 hour/day, 5 days/week over the 10-week intervention period.
- Patients will continue to perform any previously prescribed therapy.

- Once per week during this period, non-blinded study staff will employ an authorized web application on a UVA computing system to remotely monitor de-identified participant data (see Data Security Plan for details) that includes exercise adherence (duration performed), movement repetitions accomplished (exercise reps), and exercise intensity (speed).
- At least once every two weeks, non-blinded study staff will contact the participant by phone or HIPAA compliant video conferencing to collect self-reported adherence data and confirm that no change in medical status has occurred that would impact continued participation.

